HbA1c	Hemoglobin A1c
HDEC	Health and Disability Ethics Committees
ICH	International Conference of Harmonisation
QC	Quality Control
SAE	Serious Adverse Event
UADE	Unanticipated Adverse Device Effect

Site Principal Investigator Statement of Compliance

Protocol Identifying Number:	TP-0017517
Protocol Name:	Tandem Freedom Feasibility Trial #1
Protocol Version / Date:	2.0 / 30 APRIL 2024

The Principal Investigators (undersigned) hereby declare that they have read this protocol and agree to its contents.

The investigator agrees that the study will be conducted according to the applicable New Zealand regulations (Medsafe and Health and Disability Ethics Committee), International Conference on Harmonization (ICH) guidelines on Good Clinical Practice (GCP) and the principles of the World Medical Association Declaration of Helsinki 2008. The investigator will conduct all aspects of this study in accordance with all national, state, and local laws or regulations.

By written consent to this protocol, the investigators agree to the above and to fully co-operate with all monitoring and audits in relation to this trial by allowing direct access to all documentation, including source data, by authorized individuals representing Tandem Diabetes Care, Inc., HDEC, Medsafe New Zealand, and/or by the US Federal, State and local regulatory authorities.

Investigator Name: _____

Investigator Signature: _____

Date (DD/MMM/YYYY): _____

PROTOCOL SUMMARY

Study Sponsor	Tandem Diabetes Care, Inc.
Protocol Number	TP-0017517
Protocol Title	Tandem Freedom Feasibility Trial #1
Précis	This feasibility study is a prospective, single arm study evaluating the Tandem Freedom system compared to a Control-IQ technology run-in phase in adults with type 1 diabetes. Existing Control-IQ technology users will use Control-IQ technology at home for 1 week, then will use Tandem Freedom in a supervised hotel setting with Dexcom follow active. The goal of Tandem Freedom is to use the system without requiring meal boluses.
Products	Investigational Device: t:slim X2 insulin pump with Tandem Freedom Algorithm
Objectives	The objective of the study is to assess the feasibility of the Tandem Freedom system, by assessing safety and performance in a short-term supervised setting in adults with type 1 diabetes under direct clinical supervision.
Number of Sites	1 Clinical Site in New Zealand
Study Design	Single arm, prospective feasibility study to assess safety.
Number of Participants	Up to 20 participants signing consent to use the study devices, with a goal that at least 10 complete the study.
Participant Population:	
Eligibility to enroll in the study will be assessed based on the following inclusion criteria:
 
 1. Age \geq18 years old 2. Diagnosis of type 1 diabetes for at least 1 year 3. Current Control-IQ user, having been prescribed Control-IQ for at least 3 months 4. HbA1c \leq 10%, recorded in the last 3 months 5. Investigator has confidence that the participant can successfully operate all study devices and is capable of adhering to the protocol, including performing the weekend hotel observed setting portion of the study. 6. Willing to use only aspart (novorapid) or lispro (humalog) insulin with the study pump, with no use of long-acting basal insulin injections, or inhaled insulin with the study pump. 7. Have current glucagon product to treat severe hypoglycemia (injectable or nasal) at home (site will provide prescription if they do not have one) 
Eligibility to enroll in the study will be assessed based on the following exclusion criteria:
 
 1. More than 1 episode of diabetic ketoacidosis (DKA) in the past 6 months 2. More than 1 episode of severe hypoglycemia (needing assistance) in the past 6 months 3. Inpatient psychiatric treatment in the past 6 months 4. For Female: Currently pregnant or planning to become pregnant during the time period of study participation 
 a. A negative pregnancy test will be required for all females of child-bearing potential b. Counseling on appropriate birth control options will be provided to all females of child-bearing potential 5. Concurrent use of any non-insulin glucose-lowering agent, other than metformin (for example, GLP-1 agonists, Symlin, DPP-4 inhibitors, SGLT-2 inhibitors, sulfonylureas). 6. Hemophilia or any other bleeding disorder 7. Hemoglobinopathy

	
 8. History of heart, liver, lung or kidney disease determined by investigator to interfere with the study 9. History of allergic reaction to Humalog or Novorapid 10. Use of any medications determined by investigator to interfere with study 11. Significant chronic kidney disease (which could impact continuous glucose monitoring (CGM) accuracy in investigator's judgment) or hemodialysis 12. Concurrent use of any medication that could interfere with the study CGM, such as hydroxyurea 13. History of adrenal insufficiency 14. History of abnormal TSH consistent with hypothyroidism or hyperthyroidism that is not appropriately treated 15. History of gastroparesis 16. A condition, which in the opinion of the investigator or designee, would put the participant or study at risk 17. Participation in another pharmaceutical or device trial at the time of enrollment or anticipated for during the time period of study participation 18. Employed by, or having immediate family members employed by Tandem Diabetes Care, Inc., or having a direct supervisor at place of employment who is also directly involved in conducting the clinical trial (as a study investigator, coordinator, etc.); or having a first-degree relative who is directly involved in conducting the clinical trial
Participant Duration	Approximately 2 weeks

Study Endpoints	
The two study periods are:
 
 1) Control-IQ run-in period 2) The Tandem Freedom hotel observed weekend period 
Primary Endpoints for each period:
 
 1. Number of severe hypoglycemia events (with cognitive impairment such that assistance of another individual is needed for treatment) 2. Number of diabetic ketoacidosis events 3. Number of unanticipated adverse device effects 4. Number of other serious device-related adverse events 
Secondary Endpoints for each period:
 
 1. All device-related adverse events 2. CGM hypoglycemia outcomes 
 a. Overall % time <54 mg/dL b. Overall % time <70 mg/dL 3. Times in ranges-overall (70-180 mg/dL, >180 mg/dL, >250 mg/dL, 70-140 mg/dL) 4. Mean glucose 5. Glycemic variability (CV and SD) 6. Secondary endpoints 2 - 5 daytime and nighttime 
Due to the small sample size and feasibility nature of the study, primarily descriptive statistics will be used.

Protocol Overview/Synopsis	
After consent is signed, eligibility will be assessed.
 
Run-In Period: After eligibility is assessed, participants will be given a study Dexcom G6 sensor, and will continue to use their Control-IQ system for ~ 1 week at home. Participants will be instructed to bolus for meals as they normally do. Participants will be required to change their CGM sensor 48 +/- 12 hours before the hotel study.
 
Hotel Observed Session Participants will then be admitted for the hotel observed setting for 3 nights. On Day 1, participants will arrive before lunch, where they will skip a meal bolus for a meal of at least 50 grams of carbohydrates under staff supervision with their Control-IQ pump. Participants will be switched the Tandem Freedom system on the evening of Day 1, which uses a t:slim X2 insulin pump and a nearly identical interface participants are familiar with from their home pump, but is now running a new algorithm that is designed to be used without a requirement for meal boluses. Study staff will enable Dexcom follow from participants phones to study medical providers, who will also be physically present. Study staff will program the Tandem Freedom pump with open loop settings, a sleep schedule, and then enable Tandem Freedom for closed-loop. On Day 2, participants will bolus for at least 3 meals that day. At least 2 meals will have at least 50 grams of carbohydrate. The lunchtime meal will be the same as the Day 1 lunchtime meal. On Day 3, participants will not bolus for at least 3 meals that day. All meals will be similar to the prior day as much as possible. At least 2 meals will have at least 50 grams of carbohydrate. The lunchtime meal will be the same as the Day 1/2 lunchtime meal.

	
Snacks with carbohydrates will not be allowed other than for treatment of hypoglycemia, as per the study safety guidelines.
 
Participants will also perform a supervised brisk walk or similar exercise of at least 45 minutes each full day (Day 2 and Day 3), at approximately the same time each day.
 
On the morning of Day 4, participants will switch back to their home pump and complete their participation in the study.
 
No alcohol will be allowed during the hotel study.
 
Study Safety Plan:
 
Participants will use their personal blood glucose and ketone meter throughout the study.
 
Fingerstick blood glucose readings will be performed in accordance with the study protocol and as per CGM manufacturer instructions.
 
Ketone readings will be performed per the study protocol.
 
Site investigators may adjust insulin delivery profile settings as needed throughout the study in accordance with their clinical practice.
 
Real-time CGM alerts will be sent to study staff during the inpatient observed hotel phase per the study safety guidelines.

--	--

SCHEMATIC OF STUDY DESIGN

SCHEDULE OF STUDY VISITS AND PROCEDURES

Visit Number	1	2	3
Screening Visit		Control-IQ Run-In Period² 7 Days (+/- 3 days)	Hotel Study for 3 Nights
Visit (V) or Contact (C)	V	C ²	V
Informed Consent	X		
Eligibility Assessment	X		
Medical History/ physical exam	X		
Height, weight, blood pressure and pulse	X		
HbA1c (point of care or local lab) ¹	X		
Pregnancy test (females of child- bearing potential)	X		
Meal Challenge		At least 50 gram carbohydrate unannounced lunch with Control-IQ on Day 1 At least 3 announced meals with Tandem Freedom on Day 2, same lunch as Day 1	
Exercise Challenge		At least 3 unannounced meals with Tandem Freedom on Day 3, same lunch as Day 1/2 At least 45 minutes of exercise per day on Days 2 and 3	
AE/Device Issue Assessment		X ³	
Upload and Review Device Data	X	X	X

¹May use prior HbA1c value recorded in the last 3 months.

²Participants have up to 2 weeks after screening to begin the Control-IQ Run-In Period.

³Participants will call study staff for any issues related to the protocol or devices during the Control-IQ run in period.

1 Chapter 1: Background Information

2 1.1 Introduction

3 1.1.1 Disease Background

4 Type 1 diabetes affects 1.25 million people in the United States. Approximately 70% of individuals with
5 type 1 diabetes report poor metabolic control, and do not meet the American Diabetes Association's
6 recommended goal of hemoglobin A1c (HbA1c) level of 7.0%. These findings indicate the need for better
7 approaches to type 1 diabetes management.

8 1.1.2 Tandem X2 Insulin Pump and Tandem Freedom Control Algorithm

9 The Tandem X2 insulin pump with Control-IQ technology is an approved closed-loop control (CLC)
10 system. Use of the Control-IQ system has been extensively tested in adults and children with type 1
11 diabetes, demonstrating its efficacy and safety when used with insulin lispro (Humalog) or insulin aspart
12 (Novorapid).^{1,2} A recent evaluation of real-world use of the system in 9,451 users age \geq 6 years with at
13 least 12 months of system use found results comparable to those found in the randomized trials.³

14 A next generation CLC algorithm, the Tandem Freedom, is now being evaluated to remove the burden of
15 meal bolusing. The algorithm is designed to not require meal insulin boluses as part of its design. This
16 algorithm is now running in the t:slim X2 insulin pump.

17 1.2 Rationale

18 The objective of this study is to assess the feasibility of the Tandem Freedom system, by assessing safety
19 and performance in a short-term supervised first in-human study. The study will occur in a supervised,
20 hotel setting with medical staff present, with existing Control-IQ users with type 1 diabetes already
21 familiar with the t:slim X2 insulin pump, to determine how Tandem Freedom functions with unbolused
22 meals and exercise.

23 1.3 Potential Risks and Benefits

24 Risks and Benefits are detailed below. Loss of confidentiality is a potential risk; however, data are
25 handled to minimize this risk. Hypoglycemia, hyperglycemia and ketone formation are always a risk in
26 participants with type 1 diabetes and participants will be monitored for these events. As all participants
27 will be existing Control-IQ users, and familiar with infusion set care and pump use, this helps to minimize
28 risk.

29 1.3.1 Known Potential Risks

30 1.3.1.1 Blood Draw

31 A venipuncture and/or fingerstick will be performed to obtain blood for HbA1c measurement.
32 Venipuncture can cause common reactions like pain, bruising, or redness at the sampling site.
33 Less common reactions include bleeding from the sampling site, formation of a small blood clot or
34 swelling of the vein and surrounding tissues, and fainting. A fingerstick frequently causes transient pain
35 and there may be a small, localized bruise, which may be followed by a small scar that may persist for
36 several weeks. The risk of local infection is less than 1 in 1000 with either venipuncture or fingerstick.

37 **1.3.1.2 CGM and Pump Catheter Risks**

38 There is a small risk of bleeding where the sensor or infusion set is inserted. There is a small risk for
39 developing a local skin infection at the site of Continuous Glucose Monitoring (CGM) sensor placement
40 and at the pump infusion set placement. This may be associated with swelling, redness and pain; and may
41 require antibiotic therapy. Rarely, a CGM sensor may break and leave a small portion of the sensor under
42 the skin that may cause redness, swelling or pain at the insertion site.

43 Some participants may develop skin irritation or allergic reactions to the adhesives used to secure the
44 CGM, or to secure the insulin infusion sets for the continuous subcutaneous insulin infusion. If these
45 reactions occur, different adhesives or “under-taping” (such as with IV 3000, Tegaderm, etc.) will be
46 tried, sites will be rotated frequently, and a mild topical steroid cream or other medication may be
47 required.

48 **1.3.1.3 Hypoglycemia**

49 As with any person having type 1 diabetes and using insulin, there is always a risk of having
50 hypoglycemia. The frequency of hypoglycemia should be no more and possibly less than it would be
51 as part of daily living. Symptoms of hypoglycemia can include sweating, jitteriness, and not feeling well.
52 There is the possibility of fainting or seizures (convulsions) and that for a few days the participant may
53 not be as aware of symptoms of hypoglycemia. A CGM functioning poorly and significantly over-
54 reading glucose values could lead to inappropriate insulin delivery. The study exercise challenges could
55 increase the risk of hypoglycemia.

56 **1.3.1.4 Risk of Hyperglycemia**

57 Hyperglycemia and ketonemia could occur if insulin delivery is attenuated or suspended for an
58 extended period or if the pump or infusion set is not working properly. A CGM functioning poorly
59 and significantly under-reading glucose values could lead to inappropriate suspension of insulin delivery.
60 The study meal challenges and not performing premeal insulin boluses in the hotel setting could increase
61 the risk of hyperglycemia.

62 **1.3.1.5 Risk of Device Reuse**

63 All devices will be used by a single study participant only. There will be no device reuse.

64 **1.3.1.6 Potential Risks of the CLC System**

65 Even though the study system has been tested prior to this study, there is still a risk that parts of the
66 system may not function properly. The following are possible reasons the system may deliver too much
67 insulin or incorrectly stop insulin delivery:

68 • CGM sensor reads higher or lower than the actual glucose level which increases risk for
69 hypoglycemia and hyperglycemia with automated insulin delivery system;
70 • Device malfunctions that could produce a suspension of insulin delivery or over delivery of insulin.

71 **1.3.1.7 Other Risks**

72 Data downloaded from pump (to include CGM values) will be collected for the study. The downloaded
73 data from the participant's home devices at the screening visit may include data from the period beyond
74 the last 2 weeks prior to screening, although the de-identified data export will be limited to the prior 2
75 weeks. Data from the home glucose and ketone meters will be reviewed for adverse events only, and an
76 export of those devices is not required for the study. Some people may be uncomfortable with the
77 researchers' having such detailed information about their daily diabetes habits.

78 **1.3.2 Benefits**

79 Participants may achieve better glucose control than they are currently achieving using their home insulin
80 pump.

81 The individual participant may not benefit from study participation.

82 **1.3.3 Risk Assessment**

83 Based on the facts that (1) individuals with diabetes experience mild hypoglycemia and hyperglycemia
84 frequently as a consequence of the disease and its management, (2) mitigations are in place, including
85 direct medical supervision in the hotel setting and all participants are current Control-UQ users, that limit
86 the likelihood of excessive insulin dosing or prolonged withdrawal of insulin, and (3) rapid reversal of
87 hypoglycemia and hyperglycemia can be achieved, it is the assessment of the Sponsor that this protocol is
88 an investigation involving a minor increase over minimal risk. In addition, it is the belief of the Sponsor
89 that this study also presents prospect of direct benefit to the participants and general benefit to others with
90 diabetes.

91 **1.4 General Considerations**

92 The study is being conducted in compliance with the ethical principles that have their origin in the
93 Declaration of Helsinki, with the protocol described herein, and with the standards of Good Clinical
94 Practice (GCP).

95 Per Medsafe guidelines Part 11, the investigator device in the study will be labelled “To be used by
96 qualified investigators only”.

97

Chapter 2: Study Enrollment and Lead-in Period

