201 same day as the screening visit. If not completed within 2 weeks of screening, re-review of screening
202 results by the investigator should be performed, who may ask for repeated testing as per investigator
203 judgement. The device training visit must occur in clinic and cannot be performed remotely.

204 A urine pregnancy test for all females of childbearing potential (postmenarchal) who are premenopausal
205 and not surgically sterile will be completed.

206 Participants will receive additional supplies for blood glucose and ketone testing if needed. Quality
207 Control (QC) testing will be performed on the participants' meters prior to starting the run-in period.

208 Participants will continue to use their home insulin pump (t:slim X2 insulin pump with Control-IQ
209 technology) during the run-in phase. Participants will switch the CGM to the study provided CGM sensor
210 and transmitter.

211 Participants may contact study providers at any time for questions during the Control-IQ Run-In period.

212 Participants will be required to change their CGM sensor 48 +/- 12 hours before the hotel study.

213 3.2 Visit 3: Hotel Supervised Study for 3 Nights

214 3.2.1 General Guidelines

215 Upon arrival, the following procedures will be performed:

216 • Current device download of the participant's home insulin pump (with included CGM device data), for
217 the Run-In period. A de-identified CSV file will be exported from the home pump. Site will also record
218 average total daily dose, average percent basal, and average percent bolus insulin from the last 2 weeks.

219 • Assessment of device issues that have occurred.

220 • Assessment of adverse events, using open ended questions to capture hyperglycemic and hypoglycemic
221 events during the Run-In Phase.

222 For lunch on day 1 after arrival, participants will consume a meal of at least 50 gram carbohydrates, and
223 not bolus for it while wearing their home Control-IQ pump. This same meal will be used for lunch on day
224 2 and day 3.

225 After a 5 hour postprandial observation period is complete, participants will then be switched by study
226 staff to the Tandem Freedom pump (Investigational Device). Study staff will copy over pump settings
227 from the participants Control-IQ pump or make any settings changes they feel are indicated. A sleep
228 schedule will be set from 11 PM to 6 AM so sleep activity automatically activates in the evening and
229 deactivates in the morning.

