BG confirmed > 16.7 mmol/L mg/dL for more than 2 hours and ketones are < 0.6 mmol/L	
A manual correction bolus may be delivered via the pump if BG is not beginning to trend downward. Fingerstick BG and ketone measurements will be repeated after 1 hour. If a correction dose of insulin is given, the dose may be adjusted by the investigator.
 
If BG fails to decrease by a minimum of 2.8 mmol/L in 1 hour after a correction dose is given, then study staff will replace the participant's infusion set with a new infusion set and the correction bolus will be repeated per the investigator's discretion.

BG confirmed > 16.7 mmol/L for more than 2 hours and ketones are ≥ 0.6 mmol/L	A manual correction bolus may be delivered via injection to assure proper absorption in the setting of likely infusion set failure. Fingerstick BG and ketone measurements will be repeated after 1 hour. The correction dose given may be adjusted by the investigator.

	The study staff will replace the participant's infusion set with a new infusion set and the correction bolus will be repeated per the investigator's discretion. Closed loop will be disabled by the investigator for the next 4 hours and until BG has returned to <10 mmol/L.
Participant loses consciousness or has a seizure, or participant is unable to take oral carbohydrates	1 mg of IM glucagon or 3 mg nasal glucagon will be administered and 911 will be called. The study will be stopped immediately until sponsor conducts a full investigation to determine the root cause for the compromised system performance and is able to address all issues. Sponsor will also communicate the results of this root cause investigation to regulatory bodies and to study investigators.

239

240 Meal boluses and all interaction with the pump will be supervised by study staff to ensure that the correct
241 number of carbohydrate grams are entered into the bolus calculator and the correct dose is given.

242 When meal boluses are given, participants will give the bolus per their usual meal bolus timing, but not
243 more than 15 minutes before the meal.

244 No alcohol will be consumed during the hotel phase of the study.

245 At least one member of the study medical staff (Physician, NP, PA, or other qualified clinician) will
246 always be present on site.

247 During the study session, participants may change their study sensor or their infusion site as needed
248 per their usual care.

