8.1 General Statistical Considerations

649 Summary statistics will be generated for all relevant variables. In the comparison of continuous variables,
650 distributions will be tested for the normality assumption. If standard parametric techniques are found to be
651 inadequate, an appropriate non-parametric technique will be used. Categorical variables will be presented
652 using frequencies and percentages and compared using differences in proportions unless stated otherwise.
653 For safety/adverse event reporting, both the number of overall events and the number of participants
654 experiencing that event will be tabulated. No corrections will be made for multiple testing procedures.

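### For the CGM endpoints, the home Control-IQ run-in versus hotel Freedom comparison mixes the algorithm with the setting; the same-lunch contrast already built into the hotel stay is better but is not an endpoint

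*Combined protocol and SAP*

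**What the plan says.** The precis in the Protocol Summary presents a single-arm study "evaluating the Tandem Freedom system compared to a Control-IQ technology run-in phase". Its next sentence gives the order and the places: participants "will use Control-IQ technology at home for 1 week, then will use Tandem Freedom in a supervised hotel setting". The stated objective covers performance as well as safety.

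Section 8.4 names two periods, Control-IQ at home and Freedom in the hotel, and lists the same endpoints for each. The primary endpoints are safety events: severe hypoglycaemia, DKA, unanticipated device effects and other serious device-related events. Apart from device-related adverse events, the secondary endpoints are CGM measures: time below, in and above range, mean glucose and variability, overall and by day and night.

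For the run-in, the synopsis says "Participants will be instructed to bolus for meals as they normally do". For the hotel it says "Snacks with carbohydrates will not be allowed other than for treatment of hypoglycemia, as per the study safety guidelines" and "No alcohol will be allowed during the hotel study". Section 3.2.1 adds "Meal boluses and all interaction with the pump will be supervised by study staff to ensure that the correct" carbohydrate amount and dose go in. At the switch to the Freedom pump, staff may copy the Control-IQ settings or change them.

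Section 8.2 states that there are no formal hypotheses. Section 8.3 states that the sample of at least 10 completers is a convenience sample.

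**The concern.** Two columns of CGM results, one headed Control-IQ and one headed Freedom, will be read as the comparison that the precis announces. Going from one column to the other changes the algorithm and most of the participant's living conditions together. If time in range is higher in the Freedom column, the reader cannot tell whether the algorithm, the diet rules or the staff produced it. If it is lower, the exercise and meal challenges are equally good explanations. The Freedom column is also not a pure picture of the intended use, because it pools eating with boluses and eating without them. What is at stake is how the secondary CGM results of a first-in-human study are interpreted and carried into later work.

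**Working it through.** The plan gives no figure to reproduce. The check sets the two periods side by side, asks what can be separated, and compares the amount of data.

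**Step 1. Conditions in each period.**

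| Condition | Run-in (synopsis, 3.1) | Freedom period (synopsis, 3.2.1 to 3.2.4) |
|---|---|---|
| Place | Home | Hotel |
| Supervision | Participant contacts staff as needed | In person and remote, 24 hours, with the Table 1 treatment plan |
| Carbohydrate snacks | No limit stated | Barred, except to treat hypoglycaemia |
| Alcohol | No limit stated | Barred |
| Late meals | No limit stated | None once sleep activity is on |
| Exercise | None prescribed | At least 45 minutes on Days 2 and 3 |
| Boluses | As usual | Supervised. Day 1 dinner as usual, Day 2 bolused, Day 3 not bolused |
| Sleep schedule | Not specified | 11 PM to 6 AM for everyone |
| Other settings | May be adjusted | Copied or changed at the switch; may be adjusted |

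The order is fixed: home, then hotel.

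**Step 2. What can be separated.** Code each condition by an intercept and seven indicators: algorithm, place, diet rules, alcohol, exercise, bolus checking, and settings (including the sleep schedule). Home Control-IQ is (1,0,0,0,0,0,0,0) and hotel Freedom is (1,1,1,1,1,1,1,1). The matrix has rank 2 for 8 columns. The period difference estimates the sum of all seven effects, and no analysis of these two periods can isolate the algorithm.

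Add the Day 1 hotel lunch on Control-IQ: (1,0,1,1,1,0,1,0). The rank rises to 3. Hotel Freedom minus this row is (0,1,0,0,0,1,0,1), that is, algorithm + exercise + settings. Place, diet rules, alcohol and supervision cancel. Day order is not in this coding and remains.

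**Step 3. Illustration with assumed effects.** The documents give no effect sizes. Suppose the true algorithm effect on time in range is -5, 0 or +5 points and all other changes together add 0, +5 or +10. Observed difference = algorithm + other, which runs from -5 + 0 = -5 to +5 + 10 = +15. An observed +5 arises from -5 + 10, from 0 + 5 and from +5 + 0. If the other changes are unfavourable (0, -5 or -10), the range is -5 - 10 = -15 to +5 + 0 = +5, and an observed -5 arises from +5 - 10, from 0 - 5 and from -5 + 0. The sign of the period difference therefore does not give the sign of the algorithm effect.

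**Step 4. Amount and mix of data.** Assume that Day 1 lunch starts at 12:00 to 13:00, the switch comes 5 hours later (17:00 to 18:00), Day 3 breakfast is at 07:00, and the return to the home pump on Day 4 is at 06:00 to 08:00.
- Freedom time: from 6 + 48 + 6 = 60 h to 7 + 48 + 8 = 63 h.
- Run-in, 7 +/- 3 days: 4 x 24 = 96 h to 10 x 24 = 240 h.
- Share falling in 11 PM to 6 AM: 3 x 7 = 21 h, so 21/63 = 33% to 21/60 = 35% in the Freedom period, against 7/24 = 29% over full days.
- Hours from Day 3 breakfast onward: 17 + 6 = 23 h to 17 + 8 = 25 h, so 23/61 = 38% to 25/62 = 40% of Freedom time. The remaining 60% or so precedes the unbolused day.

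**Step 5. The contrast already in the schedule.** Sections 3.2.1, 3.2.2 and 3.2.4 have each participant eat the same lunch unbolused in the hotel on Control-IQ (Day 1, with 5 hours of observation) and unbolused on Freedom (Day 3). Day 2 repeats it on Freedom with a bolus. Staff record meal times, content and insulin doses. Section 8.4 does not list this contrast, and the Day 1 lunch belongs to neither of its periods: it is not at home and it is not on Freedom.

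**The case against.** The strongest reply is that the plan makes no such inference. Section 8.2 disclaims hypotheses, 8.3 disclaims power, endpoints are listed for each period rather than as a difference, and the precis itself says one period is at home and the other in a hotel. The 8.1 sentence on categorical variables, "using frequencies and percentages and compared using differences in proportions unless stated otherwise", is general and names no periods. All of this stands, and it limits the point to interpretation. It does not remove it, because the precis still names the run-in as the comparator and no section says that a period difference is not an algorithm effect.

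A reader might infer several stronger things that the documents do not support:
- That the hotel rules flatter Freedom. Sections 1.3.1.3 and 1.3.1.4 say that the exercise challenges could raise the risk of hypoglycaemia, and the unbolused meal challenges the risk of hyperglycaemia. Diet limits and checked boluses may pull the other way. The net direction is unknown.
- That settings always change at the switch. They may simply be copied, and the safety plan allows adjustment throughout the study, so in both periods. Only the sleep schedule is fixed for everyone.
- That every condition changes at the same moment as the algorithm. Participants are in the hotel on Control-IQ from before the Day 1 lunch until the evening switch.
- That participants snack and drink freely in the run-in. The plan is silent on this; it states no limits.
- That the lunch contrast is clean. It has confounders of its own, which belong next to the result.

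**Conclusion.** The point holds for the secondary CGM endpoints. The difference between the home Control-IQ period and the hotel Freedom period combines the algorithm with place, supervision, diet and alcohol limits, exercise, bolus checking, the sleep schedule and possibly other settings. The Freedom period also pools bolused and unbolused eating. The two periods cannot separate these effects at any sample size. The net bias has no size or direction that can be derived from the documents; the figures in step 3 are assumed, and the hours in step 4 rest on assumed clock times.

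A reader might go further and conclude that the safety result or the study itself is undermined. It is not: the primary endpoints are event counts reported for each period, and the study claims to be descriptive. The consequence is that the plan names a weaker contrast and leaves a better one, already carried out, without an endpoint. It should be corrected before the results are tabulated.

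**What to change.** 1. In the precis and section 8.4, state that run-in CGM values are descriptive context and that differences between home and hotel will not be attributed to the algorithm.
2. Add to 8.4, as the descriptive Control-IQ versus Freedom contrast, the within-participant 5-hour postprandial CGM summary for the identical unbolused hotel lunch on Day 1 (Control-IQ) and Day 3 (Freedom). Show the Day 2 bolused lunch alongside.
3. State the limits of that contrast: one meal; fixed day order; a morning at home before the Day 1 lunch but a probably unbolused breakfast before the Day 3 lunch; required exercise on Days 2 and 3 only; possible settings changes.
4. Report how many participants had settings changed at the switch. A separate CGM summary in those with unchanged settings is not worth adding: the group would be a small part of about 10 people, selected by staff judgment, and it would leave the home-to-hotel difference untouched.

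The cost is a few sentences, one table from CGM and meal records that the plan already collects, and a note at the switch of whether settings were changed. The documents do not say that the device exports hold settings changes, so that note may be a new item. No visit, procedure or participant is added. The sponsor gives up reading the results as Freedom compared with the run-in, and the replacement covers only a single 5-hour window.
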